## 1.5 Schema for tumour monitoring and late effects follow up.

Timing relative to diagnosis  Assessment	Post Surgery + Before RT	End of Chemo- therapy	2 yrs	3 yrs	4 yrs	5 yrs	6+ yrs	Age 20 years 
MRI and	*1	*1	*1	*1	*1	*1		
disease		q. 6 m	q. 6 m					
status dataform 12		form 12	form 12	form 12	form 12	form 12	form 12	form 12
Neurology,	*2	*2		*2		*2		*2
audiology,								
health and								
education dataforms 3, 5, & 11	forms 3, 5	form 11		form 11		form 11		form 11
Endocrin-	*3	*3	*3	*3	*3	*3	*3	*3
ology dataforms 5, 9,10	form 5	forms 9, 10	form 9	forms 9,10	form 9	forms 9, 10	form 9, and annually thereafter until 20 years old	forms 9, 10
HUI	* 5	* 5		* 5		* 5		* 6
in booklet *4								
SDQ	* 5	* 5		* 5		* 5		* 10
in booklet *4								
QoL in booklet *4	* 7	<del>*</del> 7		*7		* 7		*8

1 = MRI: After end of chemotherapy. Then at least every 6 months until 3 years post therapy. Thereafter at physician's discretion.

2 = Form 3 is for completion by neurosurgeon, forms 5, 11 by physician/nurse. For audiology, see section 4.7.6 and 10.4.4. At the end of therapy, a Pure Tone Audiogram will be performed and the Brock grading recorded on the appropriate data form or a hard copy of this audiogram sent to the National Data Centre.

3 = See Appendix M (section C) which details the minimum data to be recorded and reported.

4= HUI, SDQ and country-specific QoL forms for completion by (a) older patients and (b) a parent/carer have been compiled into age-appropriate booklets in most relevant European languages and will be supplied by national data-centres

5 = Parent and, if aged 11 years or more, patient.

6 = Patient and, if appropriate, parent/carer.

- 7 = Parent and, if > 11 years, patient. CHQ PF 28 (Germany and UK only) plus one of PedsQL or PEDQOL according to national choice Optional.
- 8 = Patient- QLQ-C30 including BN 20 in all 20 year olds— Mandatory.
- 9 = The assessment at 20 years is irrespective of interval from diagnosis and the pubertal and auxology data should be recorded annually until aged 20y. In patients enrolled after reachingthe age of 16, there will also be the assessments until 5 years from diagnosis some of which will occur past the age of 20 years.

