#### 4.7.3.1 Cross Sectional Data Collection

An additional cross sectional data collection point will be conducted starting in October 2010 to obtain a snap-shot of quality of survival data. It has been necessary to implement the collection of an additional set-of data because the quality of the data obtained so far from the longnitudial study has been poor and unanalysable. The question of quality of survival has

become even more crucial, as the emerging data suggests that there is no significant difference in event free survival between the treatment arms (Lannering, B., Rutowski, S., Doz, F., Pizer, B, Gustafsson, G., Navajas, A et al. (2010). HIT-SIOP PNET 4 – A randomised muticentre study of hyperfractaionated (HFRT) versus standard radiotherapy (STRT) in children with standard risk medulloblastoma. *Neuro-oncology*, *12*, ii5). The information obtained from the cross-section data collection will help to inform the upcoming PNET 5 and PNET 6 studies.

The assessments used in the cross-sectional data collection are listed in Appendix M.

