## 4.7.8 Hypotheses to be tested

This study will test the hypotheses that allocation to one or other treatment arm will be associated with a difference in cognition (HUI); hearing (HUI supplemented by specific audiological studies); emotion (HUI and SDQ); attention, behaviour and peer relationships (SDQ); perceived quality of life (PedsQL, PEDQOL, CHQ-PF28 or QLQ-C30 as applicable); height; sitting height; onset and progress of puberty; hormonal deficiency and glandular toxicity (gonadal and thyroid function tests) in the light of hormone supplementation. Interrelationships between endocrine function, Health Status and QoL will be examined.

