## **6.2 Post operative period** (see appendix G)

a) Cerebral MRI pre and post contrast injection.

Performed within 72 hours after surgery – Ideally between 24 and 48 hours of surgery

Postoperative scanning with MRI of brain, pre- and post-contrast, is strongly recommended in preference to CT scan with contrast, although cerebral CT scan without and with contrast injection is acceptable for local staging. The CT should be performed within 72 hours after surgery.

The size of any post operative residual tumour will be recorded.

- b) MRI of the craniospinal axis with visualisation of the end of the dural sac. (if not performed preoperatively)
- c) Lumbar puncture for CSF cytology.

Lumbar puncture should generally be performed at least 15 days following surgery, and before randomisation. If a lumbar puncture is performed before 15 days and is negative for tumour cells than this will be taken as evidence of non-metastatic disease. If, however, the CSF is positive by lumbar puncture before 15 days then the lumbar puncture will be required to be repeated at 15 days or beyond to determine M1 status.

Involvement of CSF pathways by tumour is defined as the unequivocal identification of primitive neuroectodermal cells, either on cytological grounds or with a combination of cytological and immunocytochemical features (e.g. reactivity for GFAP or a neuronal marker, such as synaptophysin).

d) Full neurological examination for neurosurgical evaluation, endocrine status and HUI, SDQ and OoL questionnaires.

To be performed after registration/randomisation and before the start of radiotherapy.

Information concerning premorbid health status and development, birthweight and parental heights, timing of puberty/menarche (where applicable) will be recorded at this time point.

- e) Audiology Pure Tone Audiometry if possible.
- f) Full blood count.
- g) Blood biochemistry electrolytes (ionogram), urea, creatinine, ALT, AST, Alkaline phosphatase, bilirubin, albumin, magnesium, calcium, phosphate).
- h) Endocrine status: Weight, standing and sitting height, Pubertal staging (Tanner), blood hormone concentrations (see Appendix M).

The PNET 4 treatment (e.g. the use of CCNU and scatter doses of radiotherapy) has the potential to affect subsequent fertility especially in males. Treating clinicians are encouraged to consider and discus this issue with patients/parents and to undertake fertility conservation measures (e.g. sperm storage) in appropriate individuals.

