# **Secondary Endpoints relating to Outcome**

We aim to test the hypothesis that treatment allocation influences cognition, hearing, behaviour, growth and/or reproductive health. The size of the groups in each of the two treatment arms is planned to be 160 children. Assuming event free survival of 75 % and 10 % loss of these survivors to follow-up, the percentage difference between prevalence of outcomes among ascertained survivors in the two HIT-SIOP PNET 4 Protocol Version 3.0, 27th July 2010 (RG\_10-034)

treatment arms that the study would have 80 % power to detect at P<0.05 is:

Outcome in ascertained survivors (n=213)	Overall % prevalence (both arms)	% difference	Numbers affected (arm A and arm B)
Cognition impaired by 2 levels (HUI)	10	10	5 vs 16
Hearing loss 40dB at 4000Hz	10	10	5 vs 16
Cognition scored abnormal (HUI)	50	20	42 vs 64
SDQ score above screening threshold	50	20	42 vs 64
Growth failure	90	12	89 vs 102

For comparison of continuous variables such as the mean number of attributes scored as 'affected' (i.e.suboptimal) between the two treatment arms, transposition of the means and standard deviations reported in the study of French children with PNET  suggests that the HIT-SIOP PNET 4 study, with 106 ascertained surviving patients in each arm, would have the power to detect a mean difference of 0.6 between the numbers of attributes affected in the two treatment arms.

Analysis of binary outcome data will make use initially of chi-squared tests in order to compare the proportions of children with specific attributes in relation to baseline, treatment-related and demographic characteristics. Further analysis will make use of logistic regression techniques. When outcomes are ordinal (i.e. mild, moderate, severe) chi squared and chi-squared for trend tests will be used initially, and further analysis will make use of ordered polytomous regression techniques. For continuous outcomes variables initial analyses will make use of parametric, i.e. t-test, or non-parametric, i.e. Mann Whitney, as appropriate. Further analyses to explore the variability of outcome, possibly after suitable transformations will use multiple regression techniques.

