## B. Audiology – see section 10.4.4 (main text)

## C. Endocrinology

#### Growth and endocrine data

#### a) At diagnosis record:

Reported birthweight (kg) Reported gestational age at birth (weeks/40) Measure parental heights (cm)

- b) At each data point (see table, Section 1.5)
  - i) Date (for calculation of decimal age)
  - ii) Auxology
    "Stretched" Standing Height (cm), "stretched sitting height (cm), Weight (kg), Pubertal ratings (as per Marshall & Tanner 1969 & 1970 (see key on data form).

Patients should have this auxology and pubertal assessment performed at least annually (from which pubertal onset can then be assessed to at least the nearest year). These data will be reported to the data centre on an annual basis.

iii) Serum Biochemistry Gonadotropins, LH (iu/L), FSH (iu/L), and Estradiol (pmol/L) (if female) or testosterone (nmol/L) (if male), Free thyroxine, T4 (nmol/L), thyrotropin, TSH (mU/L).

This biochemical assessment should be undertaken at five time points: Following surgery/before radiotherapy, at the end of chemotherapy, 3 and 5 years post diagnosis and at aged 20 years.

Measurement of gonadotrophins and sex steroids is restricted those children aged eight years or more at the time of the assessment.

Blood for LH/FSH should be timed to correspond to the follicular phase of the menstrual cycle i.e. at between Day 2 and 6 of the cycle in those women who are *spontaneously* menstruating (i.e. not on sex hormone replacement).

Measurement of free thyroxine, T4 (nmol/L) and thyrotropin, TSH (mU/L) should be undertaken in children of all ages.

iv) Hormone replacement therapy (with starting and finishing dates) or contraceptive medication.

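### Section 13.12 makes an unadjusted t-test or Mann-Whitney the initial analysis of continuous outcomes, so the arm comparison of height and sitting height gives up some precision that the pre-radiotherapy height, age and sex already collected could supply

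*Protocol*

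**What the plan says.** Protocol section 13.12, under the secondary endpoints relating to outcome, sets one rule for every continuous outcome: "For continuous outcomes variables initial analyses will make use of parametric, i.e. t-test, or non-parametric, i.e. Mann Whitney, as appropriate". The next sentence adds a second step: "Further analyses to explore the variability of outcome, possibly after suitable transformations will use multiple regression techniques". No covariates are listed for that step, and it is not described as the arm comparison.

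Section 4.7.8 lists the outcomes on which the two arms are expected to differ, including "height; sitting height; onset and progress of puberty". Section 6.2 puts the baseline measurement in the post-operative work-up: "Endocrine status: Weight, standing and sitting height, Pubertal staging (Tanner), blood hormone concentrations". The schema in section 1.5 places this before radiotherapy. Appendix M records the date at each data point so that decimal age can be calculated, and adds: "Patients should have this auxology and pubertal assessment performed at least annually". Sex is a stratification factor in section 7.

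The sample size given for continuous outcomes in section 13.12 is "with 106 ascertained surviving patients in each arm". Section 13.8 treats p-values for the secondary questions as explorative.

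**The concern.** Height SD scores before and after treatment in the same child can be expected to correlate. A two-sample test on the follow-up value leaves that shared variation in the error term. Regression on the baseline removes it at no cost in data collection, because the baseline, the dates and the sex are already on the forms. Section 13.12 nevertheless puts the unadjusted test first and leaves regression as a later exploration. No section ties the height comparison to SD scores, to change from baseline or to baseline adjustment.

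The contrast is clinically relevant. The spinal dose is 36 Gy in 1 Gy twice-daily fractions in one arm and 23.4 Gy in 1.8 Gy daily fractions in the other, and section 4.4.1 connects spinal dose with growth retardation of the spine. What is at stake is the width of the interval around the arm difference in height, not its validity.

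**Working it through.** **Inputs from the Protocol (section 13.12).** 160 per arm, 75% event-free survival, 10% of survivors lost to follow-up, 80% power, P<0.05 (taken as two-sided), and 106 ascertained survivors per arm.

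**Inputs assumed.** The correlation r between the baseline and follow-up height SD score is not in the documents; the range used is 0.3, 0.5, 0.7, 0.8. Variances at baseline and follow-up are taken as equal.

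**The plan's own figures.** 160 × 0.75 × 0.90 = 108 per arm, close to the stated 106. The stated detectable difference of 0.6 affected attributes cannot be reproduced, because its SD comes from a cited study and is not given. At 80% power it would imply an SD of 0.6 / 0.385 = 1.56. No power figure is given for height.

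**Detectable difference, in SD units of the follow-up score.**
- Follow-up t-test: (1.960 + 0.842) × √(2/106) = 2.802 × 0.1374 = 0.385.
- Change-score t-test: 0.385 × √(2(1 − r)).
- Regression on baseline: 0.385 × √(1 − r²).
- Gain: 1 − √(1 − r²) / min(1, √(2(1 − r))).

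| r | Follow-up t-test | Change t-test | Regression | Gain over the better t-test |
|---|---|---|---|---|
| 0.3 | 0.385 | 0.455 | 0.367 | 4.6% |
| 0.5 | 0.385 | 0.385 | 0.333 | 13.4% |
| 0.7 | 0.385 | 0.298 | 0.275 | 7.8% |
| 0.8 | 0.385 | 0.243 | 0.231 | 5.1% |

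**Power for a true difference of 0.30 SD, 106 per arm (noncentral t), r = 0.3 / 0.5 / 0.7 / 0.8.**
- Follow-up t-test: 0.585 throughout.
- Change t-test: 0.451 / 0.585 / 0.801 / 0.930.
- Regression: 0.625 / 0.709 / 0.861 / 0.952.

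**Missing baselines.** With a share m missing and an indicator in the model, the regression figure is 0.385 × √((1 − m)(1 − r²) + m).
- m = 0.25: 0.372 / 0.347 / 0.306 / 0.278.
- m = 0.50: 0.376 / 0.360 / 0.334 / 0.317.

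These move back towards 0.385. At r = 0.3 and 0.5, where the follow-up t-test is the better or equal comparator, the gain falls to 3% and 10% (m = 0.25), or 2% and 6% (m = 0.50). At r = 0.7 and 0.8 the change-score test also loses the patients without a baseline; its detectable difference is divided by √(1 − m). The gain over the better t-test is then 11% and 1% (m = 0.25), or 13% and 8% (m = 0.50).

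**Fewer patients.** With an assumed 60 per arm, the follow-up t-test detects 2.802 × √(2/60) = 0.511, and regression detects 0.488 / 0.443 / 0.365 / 0.307. With complete baselines the percentage gains do not depend on the number per arm.

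**The case against.** The strongest reply is that this is detail for a statistical analysis plan, which is not at hand. Section 13.12 gives a generic rule that does not mention height, allows judgement on the test, and already plans regression as a next step. An SD score or a change score could be put into the t-test without breaching the text. The only growth outcome with a power figure, growth failure, is binary and falls outside this rule.

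Most of that stands and limits the point. It does not remove it, because section 13.12 does state an order of methods, and the first-named comparison is the less efficient one for an outcome whose baseline is collected.

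Four stronger readings are tempting and are not supported.
- **Bias.** A reader might infer that the unadjusted comparison is biased. Leaving out a baseline covariate does not bias a randomised difference in means.
- **Raw centimetres.** A reader might infer that children across the whole entry age range will be compared on raw height, with a very large loss. The Protocol never says so. Likewise, a much larger gain appears if regression is set only against a follow-up t-test at high correlation, but a change-score t-test is not excluded and is the fair comparator there.
- **Age 20.** Section 1.5 notes that "The assessment at 20 years is irrespective of interval from diagnosis", and a reader might want older entrants removed from that comparison. That is a separate matter. The same note keeps the assessments up to 5 years from diagnosis for patients enrolled after 16, and any cut-off would discard data.
- **Unusable heights.** Section 4.7.3.1 reports that "the quality of the data obtained so far from the longnitudial study has been poor and unanalysable". The sentence concerns quality-of-survival data in general, and section 13.12 counts endocrine data among these, but it does not say that heights in particular are lost. It does make 106 per arm an upper limit.

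**Conclusion.** The point holds as a modest loss of precision. With up to 106 per arm and complete baselines, baseline regression lowers the detectable difference in height SD score by about 5% to 13% against the better available t-test. Regression achieves less when baselines are missing. The size rests on an assumed correlation of 0.3 to 0.8 and equal variances, neither of which the documents supply.

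The outcomes concerned are secondary, explorative and not separately powered, and adjusted analysis is already allowed as a second step. The primary event-free survival analysis and the binary growth failure comparison are untouched. The change is worthwhile because it costs so little, but it is optional.

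**What to change.** In section 13.12, state that the arm comparison of height and of sitting height is a regression of the age- and sex-standardised SD score on treatment arm, with the pre-radiotherapy SD score as covariate. Where the baseline height is missing, keep the patient and use a missing-baseline indicator. Retain the t-test or Mann-Whitney as a descriptive supplement.

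The cost is a few sentences, a reference-chart conversion for standing and sitting height, and slightly more analysis work. No additional measurements are asked of patients or centres.

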# 14. Data Monitoring and Safety Committee (DMSC)

An independent DMSC composed of 3 international experts will monitor the progress of the trial on ethical and scientific backgrounds. The role of the DMSC will be:

- to review accrual rate
- to examine interim analyses

Each interim analysis will be reported to the DMSC.

- these interim analyses will remain confidential
- on the basis of these analyses, the DMSC will recommend whether the study can continue, or whether it should be changed or terminated prematurely.

### To monitor toxicity:

- every 6 months the statistician for the trial will circulate a report to the members of the DMSC about toxicity. The DMSC will review these interim toxicity data and any relevant information will be forwarded to each Study Co-ordinator

- this biannual procedure is designed to prevent problems of major toxicity

# To examine other trials:

- the DMSC will review reports of related studies performed by other groups or organisations to determine whether such information materially affects the aims or preliminary findings of the trial
- the DMSC will be asked to review any major modification to the study proposed by the Coordinators of the trial prior to its implementation

# **Study Board**

The Study Board will be primarily responsible for conduct of the trial. The board will receive and consider relevant communications from the International Data Centre and from the DMSC and thus be responsible for major decisions affecting running of trial.

The following individuals will sit on the Study Board:

#### Appendix B

#### **International Trial Co-ordination**

The conduct of this study will be according to the following agreed procedures:

#### 1. Status of Study

This is a collaborative study between a number of participating national groups. The co-ordinators for each group are listed above (Appendix A).

#### 2. The Protocol

All national groups will use a common protocol for the international study except for HIT Group centres that will use the original HIT 2000 protocol with appropriate amendments in relation to the common study, HIT-SIOP PNET 4. The finalised master protocol in the English language will be held at the International Data Centre. Other national groups will be responsible for producing a literal translation in their own language.

Each national co-ordinator will be responsible for the distribution of protocols to centres within their national group via their national data centre as appropriate.

Appendices may be added independently by any of the national groups to address local needs, provided they have no bearing on the essential aims of the international protocol. However no change will be allowed to the eligibility criteria or the treatment procedures of the main protocol.

Subsequent to finalisation, the study chairman and the national co-ordinators must agree any amendments to the protocol.

#### 3. Study Forms

One common set of forms will be used except for the HIT Group centres who will continue to use the HIT 2000 data forms. The master version (in English) of the study forms will be held at the International Data Centre. Each national co-ordinator will be responsible for distribution of forms to centres within his/her country (using their national data centre as appropriate). Additional forms may be produced independently by any national group for the collection of data additional to that required for the international study. Subsequent to finalisation, all national groups must agree amendments to the forms. The International Data Centre will be responsible for the issue of amended forms.

#### 4. Data Collection

- a) Each national group shall hold the master database for its own patients, and shall be responsible for data quality according to local practice.
- b) The content of the database shall be identical to the data collected on the study core data forms.
- c) The master database for the entire study will be held at the International Data Centre.
- d) A complete data set will be transferred from each National Data Centre to the International Data Centre at least every six months.
- e) Forms returned from the treating institutions shall be stored at the relevant National Data Centre.

f) Data transferred from the HIT database will be made compatible with the International Database.

#### 5. Confidentiality of Patient Data

The use of names as patient identifiers on paper forms and on national databases will be according to national practice. An abbreviated patient identifier will be used for data transfer and for the master database.

#### 6. Data Quality Control

On receipt of forms at the national data centre, common range and logical checks, agreed by the study co-ordinators, will be carried out on data prior to transfer to the master database. Any amendments to the checking programme will require mutual agreement of the study co-ordinators.

Data entry verification shall be carried out according to current national practice. Cross checks of data entry will be carried out occasionally, between national centres, on a sample of forms.

Data amendments shall only be carried out at the national data centre on the national database. Errors noted on the master database, after receipt of the group database, shall be reported back to the national centre.

Data audit of study forms against the patient record forms at the treating institution shall be performed to satisfy national requirements.

